## 5.4 Procedures

### 5.4.1 Enrolment

The study nurse will visit every new-born child shortly after a CKI calls, if possible on the same day. At the home visit immediately after birth, the nurse will ask the mother of the child for confirmation of her consent for participation in the study before revealing the randomisation (for details see section 8.1). The nurse will bring a questionnaire, a study number, sticker with study number and a vaccination card.

### 5.4.2 Intervention

For all children, the nurse will examine and weigh the child, encourage skin-to-skin contact to keep the new-born warm and if necessary perform umbilical cord care. For children in the control clusters, the nurse will inform about vaccination opportunities (vaccination at closest health centre or vaccination by BHP nurse at next visit), as recommended by WHO. For children in the intervention clusters, the nurse will inform the parents that it is recommended to administer BCG and OPV at birth. If parents accept vaccination, the nurse will administer BCG and OPV, opening a vial of BCG even if there is just one child to be vaccinated (Table 1). Children in the intervention group will be vaccinated with BCG and OPV within 72 hours after birth.

#### 5.4.2.1 BCG vaccine

BCG vaccination is administered by intradermal injection; after vaccination most children develop a scar at the injection site. Among BCG-vaccinated children, having a BCG scar is associated with improved survival. The proportion of children developing a scar after BCG vaccination depends on the vaccination technique and strain. All nurses will be trained prior to the trial and supervised intensively during the beginning of the trial to ensure correct vaccination technique. The Tokyo 172 BCG strain from BCG Japan will be used for the study. The vaccine is approved by WHO and has previously been used in the national vaccination programme in Guinea-Bissau. We originally planned to use the Danish BCG strain, which has previously been used in randomised trials in Guinea-Bissau. Due to manufacturing problems at Statens Serum Institut we were not able to buy the Danish Strain used in the pilot phase of the study. We therefore decided to use the Tokyo 172 strain. The three BCG strains are currently being tested in a randomised trial at the national hospital in Guinea-Bissau.

#### 5.4.2.2 OPV vaccine

The OPV vaccine will be supplied from the national vaccination programme and thus strain, manufacturer and batch might vary. For all vaccines, the manufacturer, batch and expiration date will be registered.

### 5.4.3 Follow-up

All children enrolled in the study will receive two follow-up visits, and will be followed to 4 months of age.

#### *5.4.3.1 Follow-up in the rural regions*

The study participants will be followed through the rural HDSS, where all children below 5 years of age are followed, and information on vital status, breastfeeding status, supplementary feeding, MUAC, vaccinations, hospital admissions and whether the child has received interventions provided in campaigns is collected.

The BHP teams are accompanied by a nurse, who administers vaccines. All children have their vaccination cards examined and those missing one or more routine vaccines according to the schedule are offered these vaccines at the follow-up visits. The BHP nurse will perform the follow-up visits for the present study.

#### *5.4.3.2 Follow-up in the urban region*

The study participants will receive two follow-up visits by the study nurse at 2 and 4 months of age. The study nurse will bring BCG and OPV for children in control clusters. For the remaining routine vaccines as part of the national programme, the children will be referred to the closest health care centre. All children below the age of 3 years are followed through home visits every third month, where information on vital status, breastfeeding status, supplementary feeding, MUAC, vaccinations, hospital admissions and vaccination campaigns are collected.

### 5.4.4 Inclusion criteria

All children registered during pregnancy will be eligible for the study provided they have not yet received BCG at the date of the home visit.

### 5.4.5 Exclusion criteria

There are very few exclusion criteria, because the study is expected to answer a pragmatic question about the effect of BCG and OPV vaccination at home visits shortly after birth.

- Children born outside the cluster, and returning more than 72 hours after the delivery
- Children that the nurse evaluates to die within the next 24 hours.

## **5.5 Outcomes**

### 5.5.1 Primary outcome: Non-accidental early infant mortality

The primary outcome is non-accidental mortality between the home visit and, the next follow-up visit by the BHP, when all unvaccinated children, who are home will be offered BCG or the date, where the first non-trial vaccine is registered by BHP. All children living in intervention and control clusters will be followed through the rural or urban HDSS routines, where information on vital

status of all followed children is collected. With declining mortality, we may however not be able to obtain conclusive result. We have therefore defined the sample size for the composite outcome, but retained mortality as the primary outcome.

#### 5.5.2 Secondary outcomes

Through analyses of the secondary outcomes, we will try to gain a better knowledge of the effects of BCG and OPV. We will investigate, whether BCG and OPV affects severe morbidity:

- Non-accidental hospital admission. Hospital admission is defined as an overnight stay in a health facility. At the follow-up visits, the mother/guardian is asked, whether the child has been hospitalised. A special questionnaire is completed for each case of hospital admission to obtain information on timing, symptoms, duration and place of admission.
- Combined non-accidental mortality and non-accidental hospital admissions – severe morbidity defined as a composite outcome of mortality and first hospital admission.

Furthermore, we will assess the effect of BCG and OPV on other child-health-related outcomes:

- All-cause consultations
- Growth
  - Mid-upper-arm circumference
  - Weight-for-age z-score
- BCG scarring
- Cost-effectiveness of providing BCG and OPV at home visits
  - The cost of seeking vaccinations in rural Guinea-Bissau and the costs of consultations and hospitalisations are currently being evaluated in other studies. We will study the cost-effectiveness of providing BCG and OPV at a home visit using the effects on mortality and hospital admission from the present project.

### 5.6 Data management

Records with registration of all pregnant women will be copied from the data tables of the routine HDSS to the BCG trial data table. A list of future eligible children (pregnant women) will be printed prior to a visit to ensure that all pregnant women are invited to participate in the study. Enrolment forms will be entered to the BCG data table. Inconsistencies between the BCG trial data and the HDSS data will be checked. Main outcome events will be reviewed individually.

### 5.7 Statistical analyses

All children registered during pregnancy will enter the study when they are visited at home or 24 hours after birth, whichever comes last, thereby excluding deaths and hospital admissions on the day of birth.

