## 4 HYPOTHESIS

BCG at birth provided at a single home visit shortly after birth will reduce early infant non-accidental mortality by 40% between the home visit and the subsequent home visit or pentavalent vaccine.

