#### 5.7.6 Intention-to-treat analyses of primary outcome

We will also report intention-to-treat analyses including:

- all children, who had a home visit by a study nurse (i.e., including children who did not receive assigned treatment, children who were not enrolled because they were moribund, or who did not accept to participate).

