Appendix 2 - Planned analyses

1 Baseline

Descriptive statistics:

For eligible children visited by a study nurse within 72 hours after birth, we will describe reasons for exclusion by group allocation.

Distribution of background factors will be presented by group allocation overall and by sex and region. Background factors will be summarised by counts (percentages), means (standard deviation) or medians (interquartile range) as appropriate. Information on the proportion with missing information will be provided.

Table 1: Summary of background factors by intervention and control group

• Sex• Age at enrolment• Region• Weight at enrolment• Temperature• Mid-upper-arm circumference• Head circumference• Place of birth• Socioeconomic factors (maternal education and housing conditions)

2 Primary analysis of primary outcome

The primary analysis of early infant non-accidental mortality will be assessed on a per-protocol (PP) analysis allowing for different baseline hazards according to factors used in the randomization (Region, pre-study mortality level (high/low)) and sex, thus allowing different baseline hazards for boys and girls. To account for clustering we will employ cluster-robust variance estimates.

For the primary outcome, we will use Cox proportional hazards models that allow different baseline hazards according to the above mentioned factors and with age as underlying time-scale. Deaths due to accidents will be censored.

The primary analysis of the primary outcome is described in more detail in table 2.

Table 2: Primary analysis of primary outcome

Population	Children visited within 72 hours after birth are eligible for the study. Exclusion criteria:
------------	---

	
 - Children already BCG vaccinated - Moribund children (Expected not to survive the next 24 hours, as evaluated by the health facility nurse at the enrolment visit) - Children in rural villages where the BHP mobile teams coincidentally were in the village the same day (and vaccinated all children)
Observation period	
From: Enrolment visit or 24 hours after birth, whichever comes last
 
To: 60 days of life
 
Censoring, first of:
 
 - Visit by the BHP - 60 days - Death due to accident - Date of registering first non-trial vaccine given after enrolment - Migration (migration out of the study area as per HDSS definition)
Time scale	Age
Failure definition	Death

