Failure definition	Death due to: Malaria, Respiratory Infection, Sepsis, Gastrointestinal disease, Other
Statistical tool	Cox proportional hazards model
Stratification	We will employ models that allow for different baseline hazards according to sex, region and pre-study mortality level
Clustering	We will use robust standard errors to account for clustering within village cluster
Outline stata code For analysis: For model checking:	<pre>stset outdate, f(event==1&cause==X) enter (max(dob+1, date_enrol) /// exit (min (dnasc+60, date_mobileteam) origin(dob) stcox random, strata(sex reg prmorlev) vce(cl regam) estat phtest, detail† stphplot, strata(random) adj(sex reg prmorlev) stcox random, strata(sex reg prmorlev) vce(cl regam) tvc(random) texp(_t) *reg=region, prmorlev=pre-study mortality level, regam=village cluster</pre>

† If the proportional hazards assumption is not fulfilled we will still report the marginal hazard ratio but it will be supplemented by hazard ratios for two-three categorized time periods.

In sensitivity analyses, we will furthermore, assess whether the conclusions are robust to the following:

- Censoring follow-up at general health intervention campaigns (e.g. OPV campaigns)
- Altering the population to using an intention-to-treat approach, including all children, who had a home visit by a study nurse (i.e., including children who did not receive assigned treatment, children who were not enrolled because they were moribund, or who did not accept to participate).

- Altering the outcome from non-accidental mortality to all-cause mortality including also deaths due to accidents.
- For the non-accident hospitalisations, we will perform the analyses allowing for repeated hospitalisations. A child will return to the at-risk population the day after discharge from the hospital.

References

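### Deaths after a day-of-birth visit but before 24 hours of age fall inside the stated primary outcome yet never count, so the intention-to-treat analysis omits part of the moribund group it names as included

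*Protocol*

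**What the plan says.** **Outcome definition.** Protocol 5.5.1 states: "The primary outcome is non-accidental mortality between the home visit and, the next follow-up visit by the BHP". The hypothesis in Protocol 4 uses the same start: "between the home visit and the subsequent home visit or pentavalent vaccine".

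**Analysis window.** Protocol 5.7 lets children enter at the later of the home visit and 24 hours after birth, "thereby excluding deaths and hospital admissions on the day of birth". SAP Appendix 2, Table 2 repeats this start: "Enrolment visit or 24 hours after birth, whichever comes last". Tables 7, 8, 9 and 13 use the same wording, and the outline code sets entry at `max(dob+1, date_enrol)`.

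**Timing of visits.** Protocol 5.4.1: "The study nurse will visit every new-born child shortly after a CKI calls, if possible on the same day". Visits on the day of birth are therefore intended.

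**Intention-to-treat.** Protocol 5.7.6 adds to the analysis "children who were not enrolled because they were moribund". Under Protocol 5.4.5 these are children whom the nurse expects to die within 24 hours. SAP Appendix 2, section 5 describes the change as "Altering the population to using an intention-to-treat approach" and gives no separate start of follow-up.

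**End of window.** SAP Table 2 has "To: 60 days of life". The sample-size text in Protocol 5.3 also stops at 60 days. Protocol 5.5.1 and 5.7.3 give no such limit.

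**The concern.** The primary outcome has two starts. They differ only for children visited in the first 24 hours of life, who are the children treated as early as the protocol wants. A death in that gap occurs after treatment and inside the outcome as Protocol 5.5.1 defines it, yet it is not analysed. Protocol 1.2 reports an effect within three days of vaccination, so the early hours matter on the trial's own rationale.

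The greater stake is the intention-to-treat analysis. Whether a child is moribund is a nurse's judgement. Allocation is by cluster, and rural study nurses work at the health centre serving the cluster (Protocol 5.1.3), so a nurse may know the arm even though consent is confirmed before allocation is revealed. An analysis that puts moribund children back is a sensible safeguard. It works only if their deaths can be counted.

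**Working it through.** **1. Who is affected.**

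| Age at visit | Outcome starts (Protocol 5.5.1) | Analysis starts (Protocol 5.7, SAP Table 2) | Deaths lost |
|---|---|---|---|
| a < 24 h | a | 24 h | those between a and 24 h of age |
| 24–72 h | a | a | none through this rule |

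Of the three days after vaccination highlighted in Protocol 1.2, a visit at 6 h loses 24 − 6 = 18 of 72 hours (25%). The most that can be lost is 24 of 72 (33%).

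**2. Sample size.** The 2.4% event proportion in Protocol 5.3 is already counted from day 1. With a hazard ratio of 0.6, two-sided 5% and 80% power, events = 4(1.96 + 0.84)²/(ln 0.6)² = 120.3, rounded up to 121. Then 121/0.024 × 1.35 = 6806, about 2% above the stated 6666. This match needs 2.4% to be the proportion over both arms combined, which the text does not say. Either way the window agrees with the later start, so this point does not change the sample size.

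**3. Moribund children visited on day 0 who die within 24 h of the visit.** The documents give neither visit times nor death times, so both are assumptions here. For a visit at age a hours and death times spread evenly over the next 24 h, the share dying before 24 h of age is (24 − a)/24: 92% at 2 h, 75% at 6 h, 50% at 12 h, 25% at 18 h.

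Now average over visit ages uniform on 0–24 h. For exponential death times truncated at 24 h, with m = half-life/ln 2, the share is 1/(1 − e^(−24/m)) − m/24.

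- Even death times: 50%.
- Half-life 12 h (m = 17.3): 1/0.75 − 0.721 = 61%.
- Half-life 6 h (m = 8.66): 1/0.9375 − 0.361 = 71%.

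**4. Whole dates.** The variables `dob+1` and `date_enrol` suggest that the code uses dates rather than clock times, though the SAP does not say so. A child visited on the date of birth who dies within 24 h of the visit has a death date of dob or dob+1. Entry is at dob+1, so neither death has any time at risk, and the loss is 100%.

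**5. Illustrative loss from the primary analysis.** Protocol 2 puts about 75% of neonatal deaths in week 1. Assumptions:
- the other 25% fall on days 7–28, and days 28–60 add 15% of the neonatal total, giving 115 deaths per 100 neonatal deaths;
- day-0 visits are uniform over 0–24 h and the rest uniform over 24–72 h;
- there is no earlier censoring;
- moribund children are not excluded.

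Let f(t) be deaths per day at age t days, and p the share of children visited on day 0. The lost deaths are p × ∫₀¹ t f(t) dt. With first-week risk halving every 2 days, the integral is 11.35. Post-visit deaths are 102.3 for day-0 visits and 74.7 for later visits.

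- p = 20%: 2.27/(20.5 + 59.8) = 2.8%.
- p = 80%: 9.08/(81.8 + 14.9) = 9.4%.

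The same steps give 1–4% with flat first-week risk and 5–15% with risk halving daily.

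**6. The 60-day limit.** With rural first visits spread over 0–61 days, no deaths fall after day 60. If intervals slip to 90 days, the share is 1.9–3.6%, with the hazard after day 28 assumed to be 25–50% of the day 7–28 hazard. This is a wording matter.

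**The case against.** The late start is deliberate and openly stated. It is identical in both arms and agrees with the day 1 to day 60 window behind the sample size. Protocol 5.7.2 also describes its own text as a summary and refers to the analysis plan for detail. All of this stands. A reader might infer that the rule biases the comparison, but the documents do not support that: they show two definitions of one outcome, not a difference between arms.

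A reader might also infer that every death after a day-0 visit is lost, or that all analyses start at 24 hours. Neither is so. Under the text only deaths before 24 hours of age are lost; visits at 24–72 hours have no mismatch; and SAP Tables 10–12 (arm circumference, weight, scar) have no risk period.

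Nor is intention-to-treat the only check on the moribund exclusion. Protocol 5.7.1 reports numbers screened, eligible and enrolled by arm, and the SAP baseline section gives reasons for exclusion by arm. These would reveal an imbalance in numbers. They do not bring the deaths into the mortality comparison, which is what the intention-to-treat analysis is described as doing.

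The size is also open to challenge. It rests on assumed timing and on the nurse's prognosis being right. If moribund children are spread across visit times like the rest, with 20–80% visited on day 0, the loss among all of them is 0.2 × 50% = 10% to 0.8 × 71% = 57%. It is higher if they cluster on day 0. The 3–9% for the primary analysis is an upper-end illustration, because many children dying in the gap would already be excluded as moribund.

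**Conclusion.** The concern holds in a limited form. The primary outcome has two starting points, and for children visited on the day of birth, deaths after the visit but before 24 hours of age never count in any planned survival analysis. The intention-to-treat analysis therefore only partly includes the moribund children it names. Of those visited on day 0 who die within 24 hours of the visit, it misses about 50–71% under assumed visit and death times, and all of them if the outline code runs on whole dates. Moribund children visited later, or who survive past the start of follow-up, do enter.

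A claim that most moribund deaths overall are lost goes further than the documents allow, since they give no visit times. The effect on the primary analysis is probably small. This should be corrected, but it does not invalidate the primary analysis.

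**What to change.** 1. Keep SAP Table 2 as the primary analysis. Reword Protocol 4, 5.5.1 and 5.7.3 to its start of follow-up and its 60-day limit, which Protocol 5.3 already uses, and state the reason for the 24-hour rule.
2. Run the intention-to-treat analysis with entry at the home visit for every visited child, including moribund children and refusals. Report it beside the version with the 24-hour start, so that the effect of changing the population can be separated from the effect of changing the start.
3. Add one per-protocol sensitivity analysis of mortality and of the composite with entry at the visit and all other rules unchanged.
4. In the code for these analyses, give deaths dated on the entry date positive time at risk, for example by adding half a day, or compare the proportion dead by arm. On whole dates, moving entry to the visit date without this step would still drop same-date deaths.
5. Report post-visit deaths before 24 hours of age by arm.

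The cost is protocol and SAP wording, one further entry definition and a rule for same-date events. The sample size is unchanged. If only dates are recorded, item 5 has to be reported by date. The downside is that some very early deaths that no vaccine could prevent may move the sensitivity hazard ratios slightly toward 1.

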#### 5.7.1 Assessment of baseline distribution

Proportion of women, who gave consent during pregnancy, children visited and screened for enrolment criteria, fulfilling enrolment criteria and enrolled by trial arm will be reported.

Distribution of background factors will be described by group assignment using proportions, means and medians as appropriate.

#### 5.7.2 Analyses of outcomes

The data will be analysed on individual level data to account for varying cluster sizes. We will use the conventional 5% significance level and 95% confidence interval. Below are a summary of the planned analysis. Further details are provided in the analysis plan in the appendix.

#### 5.7.3 Primary analysis of the primary outcome

In the primary analysis of the primary outcome, we will compare the effect of BCG and OPV on early infant mortality in a Cox proportional hazards model with age as underlying time. The analysis will be performed on a per-protocol population consisting of all BCG-unvaccinated children visited within 72 hours after birth, who received the assigned treatment. Follow-up will be censored at:

- Subsequent visit by the BHP in rural areas or follow-up visits by the study nurse in the urban area, where children in the control group will receive BCG
- Date of registration of first non-trial vaccine
- Death due to accident
- Migration

#### 5.7.4 Primary analyses of secondary outcomes

We will assess the effect of BCG and OPV on severe morbidity (hospital admission and composite outcome of hospital admission and death) using Cox proportional hazards models with age as underlying time scale. We will furthermore assess the effect of BCG and OPV on the above-mentioned other secondary outcomes. The effect on growth measures will be assessed in linear regression models. To assess the effect on BCG scarring and consultations, we will use binary regression models.

#### 5.7.5 Effect modifier analyses of primary outcome

In secondary analysis, we will investigate, whether the effect of BCG+OPV differ by the following potential effect modifiers:

- Low birth weight, defined as a birth weight lower than 2500g.
  - Previous randomised trials have been limited to LBW children for whom vaccination is normally delayed. In the present trial, the majority of the children will be of

normal-birth weight (>2500g, NBW). Hence, we will assess whether LBW modifies the effect of BCG+OPV on early infant mortality and morbidity.

- Sex
  - Since we have shown sex-differential effects of vaccines, we will evaluate if sex modifies the effect of BCG+OPV on early infant morbidity and mortality.
- Maternal BCG scarring
  - Previous studies of non-specific effects suggest that maternal priming may be important for the NSEs of vaccines. Therefore, we will assess, whether the effect of OPV and BCG is modified by maternal BCG-scar status.
- Season
  - Guinea-Bissau has two distinct seasons, a dry season from December to May and a rainy season from June to November. Previous trials have indicated that the beneficial effect of BCG was particularly marked during the dry season (unpublished). We will therefore assess whether the effect in the dry season (December-May) is stronger than the effect during the rest of the year.

All analyses will be adjusted for clustering. Further details are provided in the analysis plan in the appendix.

